### *External validation analysis*

Univariable and multivariable binary logistic regression models will be used to external validate findings from the analysis within the MI-NAV WP2 material. Associations (crude and adjusted for selected covariates) between each predefined modifiable prognostic factor and costs related to 1) healthcare utilization and productivity loss, 2) healthcare utilization, and 3) productivity loss will be assessed. The cost score will be entered into the model as a dependent dichotomous variable (high cost defined as patients with cost in the top 25th percentile, yes/no). Non-linear relationships in the modelling process will be explored using cubic splines or multivariable fraction polynomials, as these are recommended approaches for modelling continuous prognostic factors in prognosis research [23]. The results will be presented as crude and adjusted odds ratios with 95% confidence intervals as shown in Table 4. The decision on whether findings from WP2 are replicated will be based on the size and direction of the association, the confidence interval, and the p-value for each of the predefined prognostic factors [24].

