### **Sample size**

This study contains secondary analyses embedded in the MI-NAV project. Details on sample size calculation are provided in the MI-NAV protocol [1]. To determine statistical power of this study we used number of events per parameter (EPP) [13-17] and the rule-of-thumb of “10 events per parameter included” [18-21]. With a fixed sample size of 509 participants included in the MI-NAV project, we anticipate 127 participants to be in the top 25th percentile of costs and categorised as having high costs (yes/no) (events). An EPP of 10 will allow a maximum of 13 parameters to be included in the final multivariable prediction model.

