### **Statistical analyses**

#### *General analysis considerations*

All analyses described in this SAP are considered a priori in that they have been defined in the protocol and/or in this SAP. All post hoc analyses will be identified as such in the article if relevant. All analyses will be carried out using SPSS, Stata, R, or other appropriate software, and controlled by a senior researcher/statistician. We consider our study as explanatory. Thus, no correction for multiple testing will be performed and p-values < 0.05 will be considered statistically significant. All statistical tests will be two-sided. All confidence intervals will be reported as 95%. Preliminary analyses assessing the influence of missing data and assumptions of normality for continuous variables will be conducted. The assumption of normal distribution will be investigated using histograms and QQ-plots. Normally distributed data will be presented with means and standard deviations (SDs), skewed data with medians and interquartile range (IQR). Categorical data will be reported as counts and percentages.

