Total			
Secondary/tertiary care			
Outpatient contact			
Day surgery			
Ordinary admission with overnight stay			
Other admissions without overnight stay			
Total			
Productivity loss			
Sick leave			
Work assessment allowance			
Disability benefits			
Total			
Total			

Cost related to productivity loss are calculated on basis of reported days with productivity loss, converted into a 5-day workweek, and adjusted for employment rate and grading of productivity loss. \*Bias-corrected and accelerated bootstrapping (1000 simulations).

**Table 4.** Binary logistic regression analyses; individual associations between modifiable prognostic factors and high costs

	High costs related to healthcare utilization and productivity loss		High costs related to healthcare utilization		High costs related to productivity loss	
	Crude OR (95% CI)	Adjusted OR* (95% CI)	Crude OR (95% CI)	Adjusted OR* (95% CI)	Crude OR (95% CI)	Adjusted OR* (95% CI)
Pain severity (NRS, 0-10)						
Self-perceived health (EQ-5D-5L, Q6, 0-10)						
Depressive symptoms (ÖMPSQ-SF, Q6, 0-10)						
Sleep quality (ÖMPSQ-SF, Q4, 0-10)						
Return to work expectancy (ÖMPSQ-SF, Q8, 0-10)						
Work satisfaction (0-10)						
Disability (EQ-5D-5L, Q3) (ref: no/slight problems)						
Moderate problems						
Severe problems/unable to do						
Health literacy (MSK-HQ, Q12) (ref: completely/very well understanding)						
Moderate understanding						
Slightly/no understanding						
Long-lasting disorder expectation (STarT MSK, Q6) (ref: no)						

EQ-5D-5L indicates EuroQol 5 dimensions; CI, confidence interval; MSK-HQ, Musculoskeletal Health Questionnaire; NRS, Numeric Rating Scale; ÖMPSQ-SF, Örebro Musculoskeletal Pain Screening Questionnaire Short Form; STarT MSK, Keele STarT MSK tool; Q, question number. \*Adjusted by sex, age, education level, absenteeism related diagnosis type, pain duration, and costs related to 1) healthcare utilization and productivity loss prior to inclusion, 2) healthcare utilization prior to inclusion, or 3) productivity loss prior to inclusion.

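### Does leaving the functional form of the six 0-10 factors open undermine Table 4 and the replication decision?

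*SAP*

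**What the plan says.** In the External validation analysis section, the SAP uses univariable and multivariable logistic regression to validate associations found in WP2. On functional form it says: "Non-linear relationships in the modelling process will be explored using cubic splines or multivariable fraction polynomials", and it justifies the two methods "as these are recommended approaches for modelling continuous prognostic factors in prognosis research". It then says: "The results will be presented as crude and adjusted odds ratios with 95% confidence intervals as shown in Table 4". Whether a WP2 finding is replicated "will be based on the size and direction of the association, the confidence interval, and the p-value", taken factor by factor.

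In Table 4, six factors are 0-10 scores with one row each: pain severity (the row beginning "Pain severity (NRS, 0-10"), self-perceived health, depressive symptoms, sleep quality, return to work expectancy and work satisfaction. Disability and health literacy have a named reference level and two level rows each. Long-lasting disorder expectation is binary.

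Two other sections bear on the point. Sample size: "With a fixed sample size of 509 participants included in the MI-NAV project, we anticipate 127 participants to be in the top 25" per cent, and "An EPP of 10 will allow a maximum of 13 parameters to be included in the final multivariable prediction model". General analysis considerations: "no correction for multiple testing will be performed and p-values < 0.05 will be considered statistically significant", with two-sided tests.

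**The concern.** A spline or fractional polynomial does not produce one odds ratio per scale. A four-knot restricted cubic spline has three coefficients, and a second-degree fractional polynomial has two coefficients and two estimated powers. Under either, the odds ratio depends on which two scores are compared, so a single row in Table 4 could not be filled and there would be no single size or direction to set against WP2.

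The SAP names two methods joined by an "or" and does not say when a curved form would replace a straight one. If the form were chosen after looking at the WP3 data, the choice could influence whether a factor counts as replicated, which is the primary aim. Some ways of choosing also raise the false-positive rate of the p-value that feeds that decision. The SAP was written after data collection ended, so prespecification carries much of the protection.

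**Working it through.** **1. The plan's own figures.** Events: 0.25 × 509 = 127.25, stated as 127. Parameters at 10 events each: 127 / 10 = 12.7, stated as 13 (127 / 13 = 9.8 events per parameter). Both reproduce, the second with rounding up.

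**2. What the table layout implies.** Where the authors wanted several contrasts for one factor, Table 4 has a reference level and separate rows. Where the factor is a 0-10 score, it has one row. One odds ratio with an interval for a numeric score is the usual display of a linear term. The text says non-linearity will be explored and then directs results to this layout. Together these describe a linearity check with the linear odds ratio reported. The clause can also cover continuous adjustment terms such as age and prior costs. A flexible form there leaves the factor's single odds ratio intact.

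**3. Parameter count.** Adjustment terms in the Table 4 footnote: sex 1, age 1, education 1, diagnosis 4 (five categories), pain duration 2 (three categories), prior costs 1 or 2 (assumed linear). Total 10 or 11.

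| Form of the 0-10 factor | Parameters | Events per parameter |
|---|---|---|
| Linear (+1) | 11-12 | 11.5-10.6 |
| Four-knot spline (+3) | 13-14 | 9.8-9.1 |
| Second-degree fractional polynomial (+4) | 14-15 | 9.1-8.5 |

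The linear form stays within the stated maximum of 13. The curved forms reach or pass it, with one exception: the four-knot spline with a single prior-cost term sits exactly at 13. If group allocation (listed under Covariates) is added with two prior-cost terms, even the linear model has 11 + 2 + 1 = 14. The count therefore supports the linear reading but does not prove it.

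**4. False-positive rates under no association.** Two simulations of unadjusted logistic models with likelihood-ratio tests, nominal 5%. Simulation A: 509 participants, 127 events, 5000 runs for each of three assumed score distributions (rounded normal with mean 6 and SD 2, uniform, right-skewed). Simulation B: 509 participants, about 25% events, 4000 runs, rounded normal with mean 5.5 and SD 2.3.

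| Rule | A | B |
|---|---|---|
| Fixed linear term | 5.0-5.2% | 4.6% |
| Pre-set four-knot spline, joint 3-df test | 4.8-5.7% | 5.4% |
| Closed second-degree fractional polynomial test (600 runs) | 1.7-2.8% | not run |
| Pre-test for curvature, then spline if p < 0.05 | 7.9-8.6% | 8.1% |
| Smallest p of linear, spline and first-degree polynomial, correct df | not run | 9.4% |
| Best first-degree power tested as if fixed in advance | not run | 12.4% |
| Smallest p with that uncorrected polynomial | not run | 14.7% |

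The Monte Carlo standard error is about 0.4 points for the 5000-run rates and about 0.6 points for the 600-run rates. The last four rows show inflation. The SAP states none of those rules.

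**5. What a fixed linear form can miss.** From simulation B with 1500 runs per assumed truth: for a doubling of the odds from a score of 7 upwards, the linear term is significant in 74% of runs and the spline in 70%. For a U-shape, the figures are 7% and 80%. A linear term loses nothing for this step-shaped, monotone relation. It does miss a U-shape, which is what the planned exploration would show.

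**The case for a change.** The strongest case for a change is that the SAP calls the two methods ways of modelling the factors, not only of checking them, and never says that the linear odds ratio is reported whatever the check shows. It treats every analysis it describes as a priori, so a form picked from the WP3 data could be presented as prespecified. In the U-shaped example the form alone decides the p-value. One sentence would close the gap at no cost in data.

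Part of this stands. The default form is not written down, and the U-shaped example is a fair warning. But the argument needs the analyst to depart from the published table layout, and a departure would be visible: a 0-10 factor with several rows, or with a curve in place of one odds ratio, would not match Table 4. It also needs an adoption rule that the SAP does not contain. Multivariable fractional polynomials are normally applied with a closed selection procedure that falls back on the linear form, and the simulated closed test stays below nominal. The rates in the working are rejection rates, not false-replication rates, since replication also weighs size and direction.

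Nor is the content of a corrective sentence available from the SAP. It would have to tie the form to the one used in WP2, which the document does not give, and any particular choice of knots would be a matter of taste.

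**Conclusion.** No change follows. The SAP leaves a detail unwritten, and its own table layout points to the sensible way of filling it: a linear odds ratio for each 0-10 score in Table 4 and in the comparison with WP2, with splines or fractional polynomials as a check on linearity. Followed that way, the p-value holds its level (4.6-5.2% simulated against 5%) and each factor has one size and direction to compare.

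The inflation of about 3 percentage points (7.9-8.6% against 5%) illustrates one possible pre-test-then-spline rule, which the SAP does not specify, and the higher rates need still looser choices. All these rates come from unadjusted models with assumed score distributions, and none measures an effect on the replication decision itself. The conclusion rests on reading the single rows as linear terms. That is the most natural reading of the layout, but it is not stated outright.

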### *Sensitivity analysis*

To assess credibility of the total cost calculation related to the primary analyses, the calculation will be conducted without outliers. Outliers will be identified with simple scatterplots by visual inspection and defined as patients with remarkably high total costs. If multiple imputation on missing data is conducted, the univariable and multivariable logistic regression analyses related to the primary analyses will be performed on complete case data to test credibility of the imputation procedure.

## **Ethics approval**

This study is a part of the MI-NAV project [1, 25]. The MI-NAV project (ClinicalTrials.gov Identifier: NCT04196634) has been classified as a quality assessment study by the Norwegian Regional Committee for Medical Research Ethics (reference no. 2018/1326/REK sør-øst A) and approved by the Norwegian Social Science Data Service (reference no. 861249) in 2018.

**Table 1.** Participants characteristics and clinical status at baseline

	All participants (n=)	Missing, n (%)
Female, n (%)		
Age in years		
Education at university level, n (%)		
Mother tongue Norwegian, n (%)		
Diagnosis (ICPC-2)*, n (%)		
Upper limb conditions		
Lower limb conditions		
Neck conditions		
Back conditions		
Joint or inflammatory conditions		
Injurie or trauma		
Other MSK conditions		
Pain severity average last week (NRS, 0-10)		
Pain duration, n (%)		
< 3 months		
3-6 months		
> 6 months		
Disability (EQ-5D-5L, Q3), n (%)		
No problems doing usual activities		
Slight problems doing usual activities		
Moderate problems doing usual activities		
Severe problems doing usual activities		
Unable to do usual activities		
Self-perceived health (EQ-5D-5L, Q6, 0-10)		
Depressive symptoms (ÖMPSQ-SF, Q6, 0-10)		
Sleep quality (ÖMPSQ-SF, Q4, 0-10)		
Health literacy (MSK-HQ, Q12), n (%)		
Completely understanding of condition/treatment		
Very well understanding of condition/treatment		
Moderately understanding of condition/treatment		
Slightly understanding of condition/treatment		
No understanding of condition/treatment		
Long-lasting disorder expectation (STarT MSK, Q6), n (%)		
Return to work expectancy (ÖMPSQ-SF, Q8, 0-10)		
Work satisfaction (0-10)		
Healthcare utilization prior to inclusion**		
Primary care consultation last 3 months, n (%)		
General practitioner		
Physiotherapist		
Chiropractor		
Emergency room		
Secondary/tertiary care last 3 months, n (%)		
Outpatient contact		
Day surgery		
Ordinary admission with overnight stay		
Other admissions without overnight stay		
Productivity loss prior to inclusion***		
Days of sick leave last 3 months		
Days of work assessment allowance last 3 months		
Days of disability benefits last 3 months		

EQ-5D-5L indicates EuroQol 5 dimensions; ICPC-2, International Classification of Primary Care 2ed edition; MSK-HQ, Musculoskeletal Health Questionnaire; NRS, Numeric Rating Scale; ÖMPSQ-SF, Örebro Musculoskeletal Pain Screening Questionnaire Short Form; STarT MSK, Keele STarT MSK tool. \*Absenteeism related diagnoses type at baseline, collected from the Norwegian Labour and Welfare Administration (NAV) registry. \*\*Collected from public records; the Norwegian Patient Registry (NPR) and the Municipal Patient and User Registry (KPR). \*\*\*Collected from the NAV registry, measured as calendar days, and adjusted for employment rate and grading of productivity loss.

**Table 2.** Healthcare utilization and productivity loss throughout 6-month of follow-up

	All participants (n=)	Missing, n (%)
Primary care		
Participants with primary care consultation, n (%)		
General practitioner		
Physiotherapist		
Chiropractor		
Emergency room		
No primary care consultation		
Numbers of consultations, median (IQR)*		
General practitioner		
Physiotherapist		
Chiropractor		
Emergency room		
Secondary/tertiary care		
Participants with secondary/tertiary care consultation, n (%)		
Outpatient contact		
Day surgery		
Ordinary admission with overnight stay		
Other admissions without overnight stay		
No secondary/tertiary care consultation		
Numbers of consultations, median (IQR)*		
Outpatient contact		
Day surgery		
Ordinary admission with overnight stay		
Other admissions without overnight stay		
Duration of ordinary admission with overnight stay in days, median (IQR)**		
Productivity loss		
Participants with productivity loss, n (%)		
Sick leave		
Work assessment allowance		
Disability benefits		
Duration of productivity loss in days, median (IQR)***		
Sick leave		
Work assessment allowance		
Disability benefits		

\*Calculated on basis of participants who have reported primary/secondary/tertiary care consultations. \*\*Calculated on basis of participants who have reported ordinary admission with overnight stay. \*\*\*Calculated on basis of participants who have reported productivity loss, converted into a 5-day workweek, and adjusted for employment rate and grading of productivity loss.

**Table 3.** Cost (€) due to healthcare utilization and productivity loss throughout 6-month of follow-up

	Participants with zero cost, n (%)	Mean (95%CI*)	Median (95% CI*)
Primary care			
General practitioner			
Physiotherapist			
Chiropractor			
Emergency room			
Total			
Secondary/tertiary care			
Outpatient contact			
Day surgery			
Ordinary admission with overnight stay			
Other admissions without overnight stay			
Total			
Productivity loss			
Sick leave			
Work assessment allowance			
Disability benefits			
Total			
Total			

Cost related to productivity loss are calculated on basis of reported days with productivity loss, converted into a 5-day workweek, and adjusted for employment rate and grading of productivity loss. \*Bias-corrected and accelerated bootstrapping (1000 simulations).

**Table 4.** Binary logistic regression analyses; individual associations between modifiable prognostic factors and high costs

	High costs related to healthcare utilization and productivity loss		High costs related to healthcare utilization		High costs related to productivity loss	
	Crude OR (95% CI)	Adjusted OR* (95% CI)	Crude OR (95% CI)	Adjusted OR* (95% CI)	Crude OR (95% CI)	Adjusted OR* (95% CI)
Pain severity (NRS, 0-10)						
Self-perceived health (EQ-5D-5L, Q6, 0-10)						
Depressive symptoms (ÖMPSQ-SF, Q6, 0-10)						
Sleep quality (ÖMPSQ-SF, Q4, 0-10)						
Return to work expectancy (ÖMPSQ-SF, Q8, 0-10)						
Work satisfaction (0-10)						
Disability (EQ-5D-5L, Q3) (ref: no/slight problems)						
Moderate problems						
Severe problems/unable to do						
Health literacy (MSK-HQ, Q12) (ref: completely/very well understanding)						
Moderate understanding						
Slightly/no understanding						
Long-lasting disorder expectation (STarT MSK, Q6) (ref: no)						

EQ-5D-5L indicates EuroQol 5 dimensions; CI, confidence interval; MSK-HQ, Musculoskeletal Health Questionnaire; NRS, Numeric Rating Scale; ÖMPSQ-SF, Örebro Musculoskeletal Pain Screening Questionnaire Short Form; STarT MSK, Keele STarT MSK tool; Q, question number. \*Adjusted by sex, age, education level, absenteeism related diagnosis type, pain duration, and costs related to 1) healthcare utilization and productivity loss prior to inclusion, 2) healthcare utilization prior to inclusion, or 3) productivity loss prior to inclusion.

